### 12.1.3. Sensitivity analyses

Missing data may have impact on the interpretation of the study results. To examine the nature of missing data, subjects who do not have HAE attack diary data completed for 28 days since the date of first dose will be listed. The number and percentage of subjects with missing data, the missing data pattern and total number of days with missing HAE attack diary data will be presented in tabular or graphical format.

Sensitivity analyses will be performed using the same ANCOVA model including the fixed term for treatment group and the adjusted qualifying attack rate(s), and for the following attack-rate scenarios:

#### 1. Attack Rate based on available Diary data

The attack rate will be derived as the total number (count) of confirmed attacks during the treatment period divided by the number of days HAE attack diary was completed. The attack rate will be calculated for each subject:

$$\text{Weekly Attack Rate} = \frac{\text{Number of Attacks} * 7}{\text{Number of days HAE Diary was completed}}$$

#### 2. Attack Rate based on Baseline observation carried forward (BOCF)

For randomized and treated subjects who have missing HAE diary data during the 28 days of planned treatment period data due to any reason, their qualifying attack rate will be carried forward (BOCF) to derive the on treatment attack rate. The attack rate will be calculated for each subject:

$$\text{Weekly Attack Rate} = \frac{(\text{Number of Attacks Reported} + \text{Number of attacks imputed}) * 7}{28}$$

Number of attacks imputed is derived based on the adjusted qualifying attack rate for the days HAE attack diary were not completed.

$$\text{Number of attacks imputed} = \frac{\text{Number of days missed} * \text{Qualifying attack rate}}{7}$$

3. Sensitivity analyses based on subject reported attacks will be performed using the similar ANCOVA model including the fixed term for treatment group and the subject reported qualifying attack rate(s) as a covariate.

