#### **10.8. Derived Attack Endpoints**

Subject-reported attacks will be adjudicated by the independent Clinical Endpoint Adjudication Panel (CEAP). The attacks that have been confirmed by the adjudication committee will be included in efficacy analyses. The details of adjudication are provided in the CEAP charter.

The attack endpoints described in this section are based on confirmed attacks by the CEAP, however the rate of attacks will also be calculated for all subject reported attacks. Efficacy analyses will be conducted for HAE attacks reported over the entire dosing period (Days 1 to 28

inclusive), during the dosing period in which BCX7353 should be at steady-state conditions (Days 8 to 28, inclusive), and during the entire study period (Day 1 to the last HAE diary in the follow-up period).

The efficacy analyses will be calculated for 3 treatment periods:

- Entire Dosing Period  
Duration (days) = 28 or (Date of last dose –date of first dose+1), whichever is earlier
- Effective Dosing Period  
Duration (days) = 21 or (Date of last dose –date of first dose-6), whichever is earlier
- Entire Study Period  
Duration (days) = Date of last HAE Attack Diary collection during the follow-up –date of first dose

All efficacy analyses will also be run by treatment period and population (FAS or PP).

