14.2.1.7	Summary of Rate of Subject-Reported Attacks during Entire Dosing Period	FAS/PP
14.2.1.8	Statistical Analysis of Rate of Confirmed Attacks during Entire Dosing Period	FAS/PP
14.2.1.8.3	Statistical Analysis of Rate of Confirmed Attacks during Entire Study Period	FAS
14.2.1.8.4	Statistical Analysis of Rate of Confirmed Attacks during Entire Study Period	PP
14.2.1.9	Statistical Analysis of Rate of Confirmed Attacks during Entire Dosing Period - Poisson-regression Model	FAS/PP
14.2.1.10	Statistical Analysis of Rate of Confirmed Attacks Requiring Treatment during Entire Dosing Period	FAS/PP
14.2.1.11	Sensitivity Statistical Analysis of Rate of Confirmed Attacks Excluding Missing Diary Days during Entire Dosing Period	FAS/PP
14.2.1.12	Sensitivity Statistical Analysis of Rate of Confirmed Attacks during Entire Dosing Period (BOCF)	FAS/PP
14.2.1.13	Statistical Analysis of Rate of Confirmed Abdominal Attacks during Entire Dosing Period	FAS/PP
14.2.1.14	Statistical Analysis of Rate of Confirmed Peripheral Attacks during Entire Dosing Period	FAS/PP
14.2.1.15	Statistical Analysis of Rate of Subject-Reported Attacks during Entire Dosing Period (subject reported qualifying rate will be used as covariate)	FAS/PP
14.2.1.16	Summary of Proportion of Subjects who are Attack-free during Entire Dosing Period (include sensitivity analyses of missing=failure; missing=excluded )	FAS/PP
14.2.1.16.3	Summary of Proportion of Subjects who are Attack-free during Entire Study Period (include sensitivity analyses of missing=failure; missing=excluded )	FAS
14.2.1.16.4	Summary of Proportion of Subjects who are Attack-free during Entire Study Period (include sensitivity analyses of missing=failure; missing=excluded )	PP
14.2.1.17	Summary of Number of Attack-free days during Entire Dosing Period	FAS/PP
14.2.1.18	Summary of Percent of Attack-free days during Entire Dosing Period	FAS/PP
14.2.1.19	Statistical Analysis of Number of Attack-free days during Entire Dosing Period	FAS/PP
14.2.1.20	Statistical Analysis of Percent of Attack-free days during Entire Dosing Period	FAS/PP
14.2.1.21	Assessment of Dose Response - Entire Dosing Period	FAS/PP
Efficacy Tables for Effective Dosing Period		
All tables will be repeated for the PP population		
Table Numbering: FAS tables will end as .1; PP tables will end as .2		
14.2.2.1	Overall Attack Summary during Effective Dosing Period	FAS/PP

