14.2.2.2	Summary of Rate of Confirmed Attacks during Effective Dosing Period (include the difference from qualifying on the same table)	FAS/PP
14.2.2.3	Summary of Number of Confirmed Attacks by Week during Effective Dosing Period	FAS/PP
14.2.2.4	Summary of Rate of Confirmed Attacks Requiring Treatment during Effective Dosing Period	FAS/PP
14.2.2.5	Summary of Rate of Confirmed Abdominal Attacks during Effective Dosing	FAS/PP

Tables	Title	Population
	Period	
14.2.2.6	Summary of Rate of Confirmed Peripheral Attacks during Effective Dosing Period	FAS/PP
14.2.2.7	Summary of Rate of Subject-Reported Attacks during Effective Dosing Period	FAS/PP
14.2.2.8	Statistical Analysis of Rate of Confirmed Attacks during Effective Dosing Period	FAS/PP
14.2.2.9	Statistical Analysis of Rate of Confirmed Attacks during Effective Dosing Period - Poisson-regression Model	FAS/PP
14.2.2.10	Statistical Analysis of Rate of Confirmed Attacks Requiring Treatment during Effective Dosing Period	FAS/PP
14.2.2.11	Sensitivity Statistical Analysis of Rate of Confirmed Attacks Excluding Missing Diary Days during Effective Dosing Period	FAS/PP
14.2.2.12	Sensitivity Statistical Analysis of Rate of Confirmed Attacks during Effective Dosing Period (BOCF)	FAS/PP
14.2.2.13	Statistical Analysis of Rate of Confirmed Abdominal Attacks during Effective Dosing Period	FAS/PP
14.2.2.14	Statistical Analysis of Rate of Confirmed Peripheral Attacks during Effective Dosing Period	FAS/PP
14.2.2.15	Statistical Analysis of Rate of Subject-Reported Attacks during Effective Dosing Period (subject reported qualifying rate will be used as covariate)	FAS/PP
14.2.2.16	Summary of Proportion of Subjects who are Attack-free during Effective Dosing Period (include sensitivity analyses of missing=failure; missing=excluded )	FAS/PP
14.2.2.17	Summary of Number of Attack-free days during Effective Dosing Period	FAS/PP
14.2.2.18	Summary of Percent of Attack-free days during Effective Dosing Period	FAS/PP
14.2.2.19	Statistical Analysis of Number of Attack-free days during Effective Dosing Period	FAS/PP
14.2.2.20	Statistical Analysis of Percent of Attack-free days during Effective Dosing Period	FAS/PP
14.2.2.21	Assessment of Dose Response - Effective Dosing Period	FAS/PP
The following will be provided for the Entire Dosing Period		
All tables will be repeated for the PP population		
Table Numbering: FAS tables will end as .1; PP tables will end as .2		

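### The only BOCF formula divides by 28 days, but Table 14.2.2.12 applies BOCF to the 21-day effective dosing period, so its absolute rates and differences would print too low

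*SAP*

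**What the plan says.** SAP 12.1.3 item 2 applies to treated subjects who "have missing HAE diary data during the 28 days of planned treatment period data due to any reason". For them, "their qualifying attack rate will be carried forward (BOCF) to derive the on treatment attack rate". The weekly rate is then the sum of reported and imputed attacks, times 7, divided by 28. No other BOCF formula is given.

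SAP 10.8 defines the length of each dosing period. For the entire dosing period: "Duration (days) = 28 or (Date of last dose –date of first dose+1), whichever is earlier". For the effective dosing period: "Duration (days) = 21 or (Date of last dose –date of first dose-6), whichever is earlier". The same section has all efficacy analyses run by treatment period, and SAP 10.8.1 divides the main weekly rate by the duration of the period in which the attacks were counted.

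SAP 16 lists BOCF for both periods. The title of Table 14.2.1.12 begins "Sensitivity Statistical Analysis of Rate of Confirmed Attacks during Entire Dosing Period (BOCF"; that of Table 14.2.2.12 begins "Sensitivity Statistical Analysis of Rate of Confirmed Attacks during Effective Dosing Period (BOCF".

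On the rate to impute, the sentence introducing the imputation formula says "Number of attacks imputed is derived based on the adjusted qualifying attack rate". The lead sentence of the item and the formula itself say only qualifying attack rate. SAP 10.3 defines a subject-reported and an adjusted version; the adjusted one merges attacks reported on consecutive days.

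**The concern.** The plan requires a BOCF table for a 21-day window but supplies a formula that is right only for a 28-day one. A programmer who restricts the counts to Days 8-28 and uses the formula as printed would divide three weeks of attacks by four weeks of time.

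A missing-data sensitivity analysis is read by setting its estimates beside those of the main analysis. If Table 14.2.2.12 differs from Table 14.2.2.8 because of the denominator, the reader cannot tell how much of the difference comes from missing diary data. A shift would appear even with no diary day missing.

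**Working it through.** **Period lengths (SAP 10.8), first dose on Day 1 and last dose on Day 28**
- Entire: 28 - 1 + 1 = 28 days.
- Effective: 28 - 1 - 6 = 21 days.

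Both match the stated lengths.

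**BOCF rate.** With A attacks reported, M days missed, q the weekly qualifying rate and D the denominator:

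rate = (A + M × q / 7) × 7 / D.

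The SAP prints D = 28. The effective period needs D = 21.

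**Reading 1: attacks and missed days both counted in Days 8-28.** The numerator is the same for either D, so the ratio is 21/28 = 0.75 for every subject.

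| A | M | q | D = 21 | D = 28 | Ratio |
|---|---|---|---|---|---|
| 3 | 0 | 1 | 1.000 | 0.750 | 0.75 |
| 3 | 5 | 1 | 1.238 | 0.929 | 0.75 |
| 2 | 7 | 1 | 1.000 | 0.750 | 0.75 |

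**Reading 2: attacks in Days 8-28, missed days over Days 1-28.** Take A = 3, q = 1 and a complete diary in Days 8-28, so the correct rate is 1.00. Let m be the days missed in Days 1-7:
- m = 0: 3 × 7/28 = 0.75
- m = 3: (3 + 3/7) × 7/28 = 0.857
- m = 7: (3 + 1) × 7/28 = 1.00

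The distortion now depends on each subject's Day 1-7 gaps. The match at m = 7 arises only because q equals the observed rate in this example.

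**Reading 3: attacks and missed days both over Days 1-28.** The arithmetic is consistent, but Table 14.2.2.12 then only repeats Table 14.2.1.12.

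**Effect on the ANCOVA under Reading 1.** Multiplying the outcome by a constant multiplies the treatment coefficient and its standard error by that constant, so their ratio is unchanged. In one simulated data set (18 per arm, some missing days), the two denominators gave:

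| D | Difference | SE | t | p |
|---|---|---|---|---|
| 21 | -0.275 | 0.150 | -1.827 | 0.077 |
| 28 | -0.206 | 0.113 | -1.827 | 0.077 |

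**Scale in trial units.** Protocol 5.3.3.3 gives interim Days 1-28 figures, used here only for illustration. A placebo rate of 0.898 per week would print as 0.898 × 0.75 = 0.674. The all-doses difference of 0.434 would print as 0.434 × 0.75 = 0.326. The relative reduction is about 48% either way (0.434/0.898 = 0.483).

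**Imputation rate.** The documents do not say how far the two qualifying rates differ. Assume 1.0 per week adjusted and 1.25 to 1.5 subject-reported. With D = 28, 14 missed days add 14 × 1.0/7 × 7/28 = 0.50 per week on the adjusted rate, and 0.625 to 0.75 on the subject-reported rate.

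**The case against.** The best defence is that item 2 is written for the 28-day planned treatment period and is correct there, while SAP 10.8 and 10.8.1 already state the general rule of dividing by the duration of the period analysed. A careful programmer might apply that rule, and a complete-diary subject printing 0.75 against 1.00 would expose the slip. SAP 11.3 also leaves room to refine computational algorithms and missing-data rules. This limits the seriousness but does not remove the point: the item prints a literal 28, and the table list calls for the effective-period version.

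A reader might infer more than the documents support:
- **That significance or the relative effect for Days 8-28 would change.** Under the uniform factor it would not, as shown above. SAP 12.1.1 also reports the relative difference from placebo, which is unaffected.
- **That every rate differs from the main analysis by a fixed 25%.** The factor of 0.75 is relative to a correctly scaled BOCF rate and requires Reading 1. Against Table 14.2.2.8 it holds only for subjects with complete treatment and complete diaries. The main analysis uses actual dosing duration for early discontinuers, and imputation itself moves subjects with missing days.
- **That the SAP prescribes two competing imputation rates, and that the choice decides which arm benefits.** The sentence introducing the formula names the adjusted rate, which is also the ANCOVA covariate. Where the other rate is meant, as in item 3, the SAP says subject reported. The shorter label is best read as a dropped adjective. Merging consecutive-day attacks can only lower a count, so the subject-reported rate could only raise or leave unchanged the imputed counts in any arm. The net effect would depend on missing days and rate gaps by arm, which the documents do not give.

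**Conclusion.** The point holds for one listed sensitivity output. As written, the plan does not yield a correct effective-period BOCF rate for all subjects. Counting attacks and missed days in Days 8-28 makes absolute rates, differences, standard errors and confidence-interval widths 25% too small; counting missed days over Days 1-28 makes the error vary by subject.

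The primary analysis, the main effective-period analysis (Table 14.2.2.8), the available-diary analysis (Table 14.2.2.11) and the entire-period BOCF table (14.2.1.12) are unaffected. What is lost is the comparison that Table 14.2.2.12 exists to support. The correction should be made, but it does not put the trial's main result in doubt. The imputation-rate label is a minor wording alignment.

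**What to change.** In SAP 12.1.3 item 2:
- Replace 28 in the weekly-rate formula with the planned length of the period analysed: 28 for the entire dosing period, 21 for the effective dosing period.
- State that reported attacks and missed diary days are both counted within that same window.
- Write adjusted qualifying attack rate in the lead sentence and in the imputation formula, to match the sentence between them.

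The cost is a text edit to the SAP and the matching line of code, best made before database lock. It needs no new data and no change to trial conduct.

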#### 12.1.4. Analysis of Secondary Efficacy Endpoints

The number and percentage of attack-free days will be analyzed similarly to the attack rate endpoint. The secondary efficacy endpoints including attack location, duration, symptoms of attacks, and number and percent of attacks requiring attack medication will be summarized for each treatment group.

The between-treatment comparisons for the weekly attack rate will be also be performed separately by attack location (peripheral or abdominal) using the ANCOVA model as described for the primary endpoint.

The attack onset relative to the time of last dose of study drug, discontinuations due to lack of efficacy and number of emergency room visits and/or hospitalizations will also be reported by treatment group.

AAS will be summarized descriptively by treatment group for each AAS question at attack level and at subject level. The most severe response from all confirmed attacks will be used at subject level summary. The between treatment group comparisons for the total AAS score and individual AAS question scores will be performed using an ANCOVA model. The adjusted qualifying attack rate will be included as a covariate.

The following additional efficacy analyses will also be performed:

- The attack rate in the pre and post treatment periods
- Time intervals between attacks

Time intervals between attacks will be derived as follows:

Subjects with no attack: Interval = duration of treatment or 28  
Subjects with 1 attack: Interval = the Max of the duration of (the first dose to start of the attack) or (stop of attack to the end of the dose )

Subjects with >1 attack: Interval = the duration between the stop of the first attack and start of the next attack (subjects with N attacks will have n-1 intervals)

- Time to first attack after the study medication

The time to first attack after the first study medication will be summarized descriptively and graphically using Kaplan-Meier method. The Kaplan-Meier (KM) estimate for the median, and the first and third quartiles will be determined along with approximate 95% confidence intervals. Brookmeyer-Crowley method will be used for the confidence interval calculation. Subjects who do not have an attack will be censored at the date of last dose for the KM analysis.

- Time to first attack after the last dose

The time to first attack after the last dose will be summarized descriptively and graphically using Kaplan-Meier method. The Kaplan-Meier (KM) estimate for the median, and the first and third quartiles will be determined along with approximate 95% confidence intervals. Brookmeyer-Crowley method will be used for the confidence interval calculation. Subjects who do not have an attack will be censored at the date of last follow-up assessment for the KM analysis.

- Time to treatment

The time to treatment defined as the time from the start of an attack to the use of the first HAE medication reported in the diary will be derived for each attack and summarized by treatment, by country and site at attack level.

The time to first HAE medication will also summarized graphically using KM method. The KM estimate for the median and the first and third quartiles will be determined along with approximate 95% confidence intervals. Brookmeyer-Crowley method will be used for the confidence interval calculation. Subjects who do not take medication will be censored at end of the attack.

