### **10.8.6. Angioedema Activity Score (AAS)**

The basis of Angioedema Activity Score (AAS) (Weller, Groffik et al. 2013) consists of 5 questions to be answered for each day during which a subject experiences an HAE attack. However, in this study, the answers to the following 4 questions will be collected for each attack:

1. How severe was the physical discomfort caused by this attack, swelling episode or HAE symptom?

2. Were you able to perform your daily activities during this attack, swelling episode, or HAE symptoms
3. Did you feel your appearance was adversely affected by this attack, swelling episode, or HAE symptoms
4. How would you rate the overall severity of this attack, swelling episode, or HAE symptoms

A score between 0 and 3 (inclusive) will be assigned to the responses for each question, and the total score for each confirmed attack will be derived as the sum of the 4 question scores. If more than 2 patient reported attacks are combined as 1 confirmed attack, the most severe response to each individual AAS question will be used for the confirmed attack.

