14.2.3.1.1	Summary of Time intervals between Attacks	FAS/PP
14.2.3.2	Summary of AAS Categorical Response -Attack level	FAS/PP
14.2.3.3	Summary of AAS Categorical Response -Subject level (worst response for each AAS question)	FAS/PP
14.2.3.4	Summary of AAS Total Score (include AAS total and Domain Total Score)	FAS/PP
14.2.3.5	Statistical Analysis of AAS Total Score (include AAS total and Domain Total Score)	FAS/PP
14.2.3.6	Summary of Attack Duration at Subject Level – Confirmed Attacks	FAS/PP
14.2.3.7	Summary of Attack Duration of All Confirmed Attacks	FAS/PP
14.2.3.8	Summary of Attack Triggers – Confirmed Attacks	FAS/PP
14.2.3.9	Summary of Attack Symptoms – Confirmed Attacks	FAS/PP
14.2.3.10	Summary of Number of Symptoms – Confirmed Attacks	FAS/PP

Tables	Title	Population
14.2.3.11	Summary of Attack Location – Confirmed Attacks	FAS/PP
14.2.3.12	Summary of Attack Onset time from the last dose– Confirmed Attacks	FAS/PP
14.2.3.13	Summary of Administrations of Acute HAE Medications – Confirmed Attacks	FAS/PP
14.2.3.14	Number and Percentage of Attacks Requiring Additional Medical Care	FAS/PP
14.2.3.15	Summary of time to treatment –Confirmed Attacks (overall, by country and by site )	FAS/PP
14.2.3.16	Time to Treatment (KM estimates)	FAS/PP
14.2.3.17	Summary of Qualifying, Screening Attack and Post Treatment HAE attack Rate	FAS/PP
14.2.3.18	Statistical Analysis of Post Treatment HAE attack Rate	FAS/PP
14.2.3.19	Time of First Attack after the First Dose (KM estimates)	FAS/PP
14.2.3.20	Time of First Attack after Last Dose (KM estimates)	FAS/PP
14.2.4.1	Summary of AeQoL scores	FAS/PP
14.2.4.2	Statistical Analysis of AeQoL Scores	FAS/PP
14.2.4.3	Correlation among AeQoL and Attack Rate	FAS/PP
14.2.4.4	Summary of DASS Severity-Rating Index Categories	FAS/PP
14.2.4.5	Summary of DASS scores	FAS/PP
14.2.4.6	Correlation among DASS Domains and Attack Rate	FAS/PP
14.2.4.7	Correlation between AeQoL and DASS Domains	FAS/PP
14.2.5.1	Statistical Analysis of DASS Scores	FAS/PP
Pharmacokinetic Analysis		
14.2.5.2	Summary of Plasma BCX7353 Concentration	PK
14.2.5.3	Summary of Derived Plasma BCX7353 Pharmacokinetic Parameters	PK
14.2.5.4	Summary of Trough BCX7353 Concentration	PK
14.2.5.5	Assessment of Dose Proportionality based on Power Model	PK
14.2.5.6	Assessment of Dose Proportionality based on ANOVA	PK
14.2.5.7	Assessment of Steady State	PK
14.2.5.8	Number and Percent of Average Ctrough above 4xEC50 and 4xEC80	PK

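### The ANCOVA on AAS scores has no stated unit of analysis and no rule for attack-free subjects, and neither direct reading of it gives a valid between-group comparison of attack severity

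*SAP*

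**What the plan says.** SAP 10.8.6 collects AAS per attack: "the answers to the following 4 questions will be collected for each attack". Items are scored from 0 to 3 and added up within an attack: "the total score for each confirmed attack will be derived as the sum of the 4 question scores". The total therefore runs from 0 to 12 and is defined only where there is a confirmed attack. No section gives a value to a subject without one.

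SAP 12.1.4 plans descriptive summaries at attack level and at subject level. For the latter, "The most severe response from all confirmed attacks will be used at subject level summary". The next sentence moves to inference: "The between treatment group comparisons for the total AAS score and individual AAS question scores will be performed using an ANCOVA model". The only covariate named is the pre-treatment adjusted qualifying attack rate. No unit of analysis, within-subject term or handling of attack-free subjects is given.

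In the output list (SAP section 16) the worst response appears in the title of one categorical table: "Summary of AAS Categorical Response -Subject level (worst response for each AAS question". The inferential table for the AAS total score, 14.2.3.5, names no unit.

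The rule for merged attacks in 10.8.6 begins "If more than 2 patient reported attacks are combined as 1 confirmed attack". A merge of exactly two reports has no AAS rule, although 10.8.4 sets the threshold for attack duration at more than one report.

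**The concern.** Having a confirmed attack is a post-randomisation outcome and is what the primary endpoint counts. An ANCOVA on available scores compares subsets that treatment helps to create. The covariate is the pre-treatment attack rate and cannot undo that.

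Two further faults depend on the unit. A maximum over attacks rises with the number of attacks, so a drug that only prevents attacks would look as if it made them milder. With one row per attack, several rows from one subject would be treated as independent.

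At stake is a nominally significant statement about attack severity, tested two-sided at 0.05 without multiplicity adjustment (SAP 12.1.1), that could not be interpreted. The gap is specific to AAS. The same section sets rules for attack-free subjects in the interval and time-to-first-attack analyses, and 10.8.2 gives three ways of handling early discontinuation in the attack-free endpoint.

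**Working it through.** **Inputs from the documents.** Treatment lasts 4 weeks. The SAP power tables supply design rates of 0.7 or 0.8 (placebo) and 0.3 (active) attacks per week, and attack-free shares. Protocol 5.3.3.3 gives interim rates: placebo 0.898, 350 mg 0.898 − 0.384 = 0.514, 125 mg 0.898 − 0.579 = 0.319.

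**Assumed, because the documents give no AAS data.** Score distributions; within-subject correlation 0 to 0.5; Poisson counts in steps 1 to 3; in step 4, active SDs of 0.45 (350 mg) and 0.3 (125 mg) at the interim rates, and 24 vs 14 subjects in the 125 mg comparison.

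**The plan's own figure.** The SAP states no figure for AAS. Its power row 0.7 (SD 0.45) vs 0.3 (SD 0.3), 18 per arm, stated as 86%, reproduces at 85.9% with an unequal-variance t-test.

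**1. Who is scored.** With 18 per arm, placebo 20–30% attack-free leaves 18 × 0.70 to 18 × 0.80 = 12.6 to 14.4 subjects with a score. Active 70–85% attack-free leaves 18 × 0.15 to 18 × 0.30 = 2.7 to 5.4. Under Poisson counts at 0.7 vs 0.3 per week, the scored share is 1 − e^(−2.8) = 94% vs 1 − e^(−1.2) = 70%, with 2.8/0.94 = 3.0 vs 1.2/0.70 = 1.7 attacks per scored subject.

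**2. Why the maximum shifts.** Take each item uniform on 0–3 and attacks independent. The expected worst item over k attacks is 3 − (0.25^k + 0.5^k + 0.75^k). Times four items, that is 6.0 for k = 1, 8.5 for k = 2 and 9.75 for k = 3, with severity unchanged. Averaging over Poisson counts of at least one:

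- 0.7 vs 0.3 per week: 9.1 vs 7.5, difference 1.6
- 0.898 vs 0.514: 9.7 vs 8.4, difference 1.3
- 0.898 vs 0.319: 9.7 vs 7.6, difference 2.2 before rounding

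Across three assumed item distributions the ranges are 1.3–1.6, 1.1–1.3 and 1.7–2.2.

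**3. Alternative severity assumption.** Per-attack total with mean 6 and SD 2.5, rounded to 0–12, identical in all arms; worst attack among scored subjects:

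| Within-subject correlation | Placebo 0.898 | 350 mg 0.514 | 125 mg 0.319 | Spurious differences |
|---|---|---|---|---|
| 0 | 8.1 | 7.3 | 6.9 | 0.8 and 1.3 |
| 0.5 | 7.5 | 6.9 | 6.6 | 0.6 and 0.9 |

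Unscored subjects are 3%, 13% and 28% in the three arms.

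**4. Error rates.** Simulation with 2000 trials per setting, four correlated items, within-subject correlation 0.1 to 0.5, and severity identical in both arms and independent of attack count. A two-sample t-test stands in for the ANCOVA because the covariate is pre-treatment.

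| Rates per week; subjects | Shift in worst score | Rejects: worst score | Rejects: one row per attack | Rejects: subject mean |
|---|---|---|---|---|
| 0.7 vs 0.3; 18 vs 18 | 0.8–1.2 | 11–23% | 9–18% | 5–6% |
| 0.8 vs 0.3; 18 vs 18 | 1.1–1.5 | 14–35% | 9–18% | 4–6% |
| 0.898 vs 0.514; 20 vs 18 | 0.8–1.0 | 10–22% | 12–23% | 5–6% |
| 0.898 vs 0.319; 24 vs 14 | 1.3–1.7 | 20–43% | 8–17% | 7–8% |
| equal rates | about 0 | 5–6% | 12–24% | 5% |

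The worst-score excess vanishes at equal rates, so it comes from attack frequency. The one-row-per-attack excess does not vanish, so it comes from clustering. The subject mean removes both, but attack-free subjects still drop out.

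**5. What a zero-filled cumulative score measures.** With λ expected attacks, mean 6 and SD 2.5 per attack, and independence, the total has mean 6λ and variance λ(6² + 2.5²) = 42.25λ. For λ = 3.592, 2.056 and 1.276 the means are 21.6, 12.3 and 7.7, and the variances 151.8, 86.9 and 53.9. The standardised differences from placebo are 9.2/10.9 = 0.84 and 13.9/10.1 = 1.37, with no severity effect at all. This is a burden measure.

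**The case against.** A reader might infer that the SAP tests each subject's worst response. The text does not say so. The rule is tied to the descriptive subject-level summary and one categorical table, while the total score is defined per attack. On the attack-level reading the shift towards milder scores disappears. This stands, and the worst-score result is therefore conditional. The subject-level reading remains the natural one, since the covariate is a subject-level value and no within-subject term is planned. The attack-level reading also fails, through clustering.

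The size is not fixed by the documents. The severity distribution and within-subject correlation are assumed, and higher correlation shrinks the shift. This stands; only the direction follows from taking a maximum.

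A reader might also infer that selection alone biases the result in a known direction, for example that preventing mild attacks would make severity look worse. That needs severity to be related to frequency or response, and the documents give no data on it.

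Scoring attack-free subjects as 0 makes the result depend even more on frequency. This is correct, and such a score must not be read as severity.

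The study plans no formal hypotheses (Protocol 13.2.4), the SAP takes an estimation approach (7.1), and AAS is a comparison to be made if data permit (7.2). This lowers the importance but does not validate the p-values.

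On the merge rule, nothing shows how often exactly two reports are combined, and 10.8.4 makes the intent fairly plain. It is a wording gap.

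**Conclusion.** The concern holds in a conditional form. The SAP plans a between-group ANCOVA on a score that exists only for confirmed attacks, and states neither the unit nor the handling of attack-free subjects.

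If the worst response is tested, lower attack frequency alone produces a difference in favour of active: about 0.6 to 1.3 points under mean 6, SD 2.5 and within-subject correlation 0 to 0.5, and up to about 2 under other assumed item distributions. False-positive rates are roughly 10–40% against 5%. If each attack is a row, they are about 10–25% even with equal attack rates.

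Both readings compare only subjects with a post-randomisation attack, with an unknown bias from that selection. These sizes rest on assumed score distributions and correlations. The fault should be corrected, but it concerns a secondary comparison; the primary attack-rate analysis is untouched.

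**What to change.** In SAP 12.1.4, and in the output list where needed:

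1. Do not test the worst-response score. Keep worst-response and per-attack AAS descriptive, and show how many subjects are scored in each arm.
2. If a randomised comparison is wanted, test a per-subject cumulative AAS over the dosing period in the FAS, with attack-free subjects scored 0. Label it attack burden, not severity.
3. If severity given an attack is compared, use the subject's mean over attacks or a model with a subject random effect. Label it as conditional on having an attack.
4. In 10.8.6, apply the merge rule to two or more reports, in line with 10.8.4.

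The cost is a few sentences and no new data; SAP 11.3 already allows computational algorithms and rules for unclear data to be refined. The downside is that the burden score overlaps with the attack-rate endpoint, so the per-attack description has to stay beside it.
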